## LIST OF ABBREVIATIONS AND DEFINITIONS OF TERMS

Abbreviation	Definition
AE	adverse event
EE	efficacy evaluable
MedDRA	Medical Dictionary for Regulatory Activities
MITT	modified intent-to-treat
NASID	non-steroidal anti-inflammatory drug
PT	preferred term
SOC	system organ class
TEAE	treatment emergent adverse event

## 1 Introduction

Topical Remedy, LLC is developing Merlin, a novel topical formulation that can be used to treat viral infections of the skin. It is composed of two commonly used compounds, glycolic acid (0.6%) and ethanol (10%), each with known safety and side effect profiles. This product, intended for over-the-counter distribution, will consist of single treatment foam applicators pre-filled with the Merlin solution.

## 2 Trial Design

### 2.1 Study Objectives

The primary objective of this study is to assess the efficacy of Merlin solution on the clinician assessed duration of the classical herpetic lesion as compared to placebo treatment. Duration is based on staging of the lesion. Staging is graded as follows: 0=prodromal, 1=erythema, 2=papula/edema, 3=vesicle/pustule, 4=ulcer/soft crust, 5=hard crust, 6=residual swelling/dry flaking, 7=normal skin. The duration of a classical lesion is defined as the time, in hours, from the beginning of treatment to the onset of Stage 6, or, if Stage 6 is never observed, Stage 7. A classical lesion is defined as one that progresses through any of stages 3, 4 or 5.

The secondary objectives of this study are to compare the active and placebo treatment groups with regard to:

- clinician assessed
  - duration of the herpetic episode (classical and non-classical)
  - duration until complete healing of the herpetic episode (classical and non-classical)
  - prevention of progression to a classical lesion
  - maximum lesion area of the classical lesions
  - cumulative lesion area of the classical lesions
  - cumulative lesion area of all lesions
  - duration of classical herpetic lesion hard scab
- safety

Based on patient diary entries, other objectives of this study are to compare the active and placebo treatment groups with regard to:

- subject assessed:
  - duration of the classical herpetic lesion
  - duration of the herpetic episode (classical and non-classical)
  - duration of complete healing of the herpetic episode (classical and non-classical)
  - prevention of progression to a classical lesion
  - duration of classical herpetic lesion hard scab
  - severity of lesion pain
  - duration of lesion pain

## 2.2 Study Design

This current clinical study is a Phase 2 trial using the same Merlin formulation as was used in the Phase 1 TR-H-111 and Phase 2 TR-H-211 trials. This trial will have two treatment groups comparing the safety and efficacy of Merlin solution to that of a placebo (10% ethanol) with treatment at first visible signs of a herpetic episode.

The present trial is designed to examine the efficacy and safety of treatment with Merlin as compared to treatment with placebo (10% ethanol) in subjects treating at first visible signs of a herpes labialis lesion (i.e. erythema [Stage 1] or papule/edema [Stage 2]).

Approximately four hundred and fifty (450) subjects will be enrolled into the study, with a goal of approximately one hundred and fifty (150) of these subjects who will actually enter the Treatment Phase of the study. Eligible subjects will be randomized in a 1:1 ratio to one of two treatment groups:

- 1) treatment of three (3) applications of Merlin solution or
- 2) treatment of three (3) applications of 10% ethanol, as a placebo,

performed within a time period of 40 minutes or less, while allowing time for the solution to dry on the lesion between applications.

A total of twelve (12) Merlin or placebo treatments, i.e. thirty-six (36) applications, will be administered over the ensuing ninety-six (96) hours (four (4) days) after the first treatment. On each day, treatments will be administered six (6) hours apart, with a maximum of three treatments each day. The first treatment will be administered on Treatment Day (Day 0), and then repeated at 6 and 12 hours after the first treatment, time permitting.

After being enrolled and randomized into the study, subjects will be sent home with a sealed kit for either Merlin (active) or 10% ethanol (placebo). At first signs and/or symptoms of a recurrent herpetic episode (Stage 0, prodrome Stage 1, erythema, or Stage 2, papule/edema), subjects will call the clinic to confirm by telephone interview, the presence of a lesion and the lesion stage. Subjects reporting either a Stage 1 or Stage 2 lesion will be interviewed to review the eligibility criteria. If they meet all the eligibility criteria they will then be instructed to begin treatment immediately, thereby initiating the Treatment Phase of the study. Subjects will then be instructed to return to the clinic as soon as possible within 24 hours of starting treatment. Subjects reporting only Stage 0 symptoms, i.e. no visible signs of a cold sore lesion, will be instructed to monitor their lesion and to call the clinic immediately upon observing any early visible sign of a cold sore, i.e. a Stage 1 or Stage 2 lesion.

Subjects will report daily for a minimum of 3 consecutive days, with the last clinic visit at the time of complete healing (Stage 7 - normal skin) or at 14 days, whichever is earlier. Subjects will be contacted by phone, for a safety assessment, 2 weeks after they complete the Treatment Phase of the study. Subjects will also be provided a diary that he or she will be instructed to fill out daily from the first day of treatment until their final clinic visit.

Both treatment groups will continue to accept subjects into the Treatment Phase of the study until there are at least seventy five (75) subjects in each group.

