After being enrolled and randomized into the study, subjects will be sent home with a sealed kit containing a bottle filled with either Merlin (active) or 10% ethanol (placebo) and a packet of foam-tipped applicators sufficient to apply three study treatments (nine (9) applications). At first signs and/or symptoms of a recurrent herpetic episode (Stage 0, prodrome Stage 1, erythema, or Stage 2, papule/edema), subjects will call the clinic to confirm by telephone interview, the presence of a lesion and the lesion stage. Subjects reporting either a Stage 1 or Stage 2 lesion will be interviewed to review the eligibility criteria. If they meet all the eligibility criteria they will then be instructed to begin treatment immediately, thereby initiating the Treatment Phase of the study. Though subjects reporting a Stage 2, papule/edema, lesion will be allowed to treat, subjects should be strongly encouraged to call at the first visible signs of a herpetic lesion. A subject observing a lesion at Stage 1, erythema, therefore, should call in immediately rather than assume they may wait until their lesion reaches Stage 2, papule/edema, to call in. Subjects reporting only Stage 0 symptoms, i.e. no visible signs of a cold sore lesion, will be instructed to monitor their lesion and to call the clinic immediately upon observing any early visible sign of a cold sore, i.e. a Stage 1 or Stage 2 lesion. Once the subject calls in and confirms by telephone interview that their lesion has reached Stage 1 or 2, and that they still meet all eligibility criteria, they will be instructed to begin treatment immediately. Subjects will then be instructed to return to the clinic as soon as possible within 24 hours of starting treatment.

Subjects will report daily for a minimum of 3 consecutive days, with the last clinic visit at the time of complete healing (Stage 7 - normal skin) or at 14 days, whichever is earlier. Subjects will be contacted by phone, for a safety assessment, 2 weeks after they complete

the Treatment Phase of the study. Subjects will also be provided a diary that he or she will be instructed to fill out daily from the first day of treatment until the lesion is healed.

Both treatment groups will continue to accept subjects into the Treatment Phase of the study until there are at least seventy five (75) subjects in each group. Once the enrollment objectives for the Treatment Phase of the study have been met, the study will be closed to any further enrollment.

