## 7.2.5 Subject Diaries

Each subject will be instructed to record into their diaries the date and time of their first treatment, the stage of their lesion, and his or her assessments of pain as described in this section. The recording of the assessments of lesion stage and pain level are to be done three times per day, just prior to initiation of each treatment (i.e. just prior to the first application in a set of three (3) applications). After the course of treatment is completed, assessment of lesion stage and pain level will continue 3 times daily with approximately 6 hours in between each assessment until the lesion is healed. The subject will also be instructed to bring the diary to each office visit so that the Investigator or trained designee can review it.

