### **7.3 Follow-up Visits (Visit Days 1-14)**

Each subject entered into the Treatment Phase of the study is to come in for an office visit every day, (preferably about the same time of day each day, if possible), following treatment until the clinician or trained designee determines that the treated lesion has reached Stage 7, up until at least Visit Day 3 and at most until Visit Day 14. As subjects might call any time of the week, and the Treatment Phase of the study could last as many as 14 days, clinics must be staffed with personnel, trained in lesion assessment, 7 days a week. Every effort should be made to get the subject to come to all their study visits. If a subject misses a visit, the study clinic visits still end for them on Visit Day 3 if their lesion has reached Stage 7 by then, or on the day their lesion reaches Stage 7, or Visit Day 14, whichever comes first.

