A herpetic lesion typically progresses to higher level stages and therefore would not be expected to proceed from a higher number stage to a lower number stage. The exception to this would be the case where a subject has a Stage 5, hard crust, lesion in which the scab is inadvertently knocked off, e.g. while washing. In that instance, the lesion would “go backwards” from a Stage 5 lesion to a Stage 4. This expected progression of the herpetic lesion should be kept in mind as a guideline in the evaluation of the lesion stage. Any time, therefore, a lesion is observed to “go backwards,” a note should be made in the CRF as to why, if the reason can be determined, the lesion reversed its progression.

The study clinic visits end for a subject when (1) the treated lesion is no longer present (Lesion Stage 7 for both classical and non-classical lesions) and there have been clinic assessments every day up until at least Visit Day 3, or (2) at Visit Day 14, whichever occurs earlier.

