#### **10.7.3 Duration until Complete Healing of the Herpetic Episode (clinician and patient assessed)**

Duration until complete healing of the herpetic episode is defined as the time, in hours, from the beginning of treatment to the onset of Stage 7, for both classical and non-classical lesions. All subjects will visit the clinic daily, for a minimum of 3 days and a maximum of 14 days, until the lesion reaches Stage 7 with no signs or symptoms of a herpetic lesion.

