## 8 Handling of Missing Data

All missing data will be queried. Missing efficacy data on duration endpoints for subjects in the MITT Population which are not retrievable through queries will be handled using imputation of 336 days. Other missing data, including missing safety data, will not be imputed.

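### SAP 2.2 ties the end of the diary to the clinician's Stage 7, and no consistent rule covers a fully followed subject whose own last recorded stage is below 7

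*SAP*

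**What the plan says.** **When the diary ends.** SAP 2.2 says that subjects are "instructed to fill out daily from the first day of treatment until their final clinic visit". Protocol 4 says instead that they are "instructed to fill out daily from the first day of treatment until the lesion is healed", and Protocol 7.2.5 that after treatment "assessment of lesion stage and pain level will continue 3 times daily with approximately 6 hours in between each assessment until the lesion is healed". Neither Protocol section names the assessor whose judgement of healing counts. In both schedules of events (Protocol Table 7-1, SAP 5), footnote 2, which sets the daily follow-up and the last clinic visit, is attached to the Subject Diary row.

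**Who fixes the final visit.** Protocol 7.3 runs visits "until the clinician or trained designee determines that the treated lesion has reached Stage 7", with Visit Day 3 as the minimum and Visit Day 14 as the maximum. Protocol 7.3.1 agrees: "The study clinic visits end for a subject when (1) the treated lesion is no longer present".

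**What the endpoint needs.** Time to complete healing, clinician and patient assessed, runs "from the beginning of treatment to the onset of Stage 7, for both classical and non-classical lesions" (Protocol 10.7.3; SAP 6.1.4 has the same definition). Episode duration for an aborted lesion also ends at Stage 7.

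**Missing durations.** SAP 8 says: "Missing efficacy data on duration endpoints for subjects in the MITT Population which are not retrievable through queries will be handled using imputation", and prints the value as 336 days. SAP 7.13.1 and 7.1.2 describe a narrower scope, compared below.

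**The concern.** The subject-assessed durations are meant to be a second reading of healing, taken from the diary. Under the SAP the clinician's score decides when that reading stops. If the subject has not yet recorded Stage 7, the event time was never collected, although the subject attended every visit.

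At stake is what the analysis then does with a completer. Entering the maximum duration would be wrong for that subject and would weaken or shift the group comparison. Leaving the value missing removes the subject from an analysis described as one of complete cases. The documents do not say consistently which happens.

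**Working it through.** **Step 1. Can the missing Stage 7 be recovered?** Not by any stated route. Protocol 7.3.2 bars retroactive diary changes and has blanks marked so that they cannot be filled later. Protocol 7.4 describes the two-week call as a safety evaluation only. No diary collection after the last visit is described.

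**Step 2. Which endpoints are exposed?** Subject-assessed complete healing (all lesions) and subject-assessed episode duration (aborted lesions), since both end at Stage 7. Classical-lesion and hard-scab durations normally end at Stage 6, and progression and pain severity do not use Stage 7.

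**Step 3. Which missing-data rule applies to this completer?**

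| Place | Scope of the rule | Result |
|---|---|---|
| SAP 7.13.1, SAP 7.13.5 matrix, Protocol 10.7 matrix | MITT durations, subjects who leave before healing | Not reached: the subject did not drop out |
| SAP 7.1.2 | MITT imputation confined to the primary endpoint | No diary endpoint is imputed |
| SAP 8 | Any irretrievable MITT duration | Imputed, at 336 days as printed |
| SAP 7.1.3 and 7.13.1, EE | Observed values only; described as complete cases | Value missing |

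**Step 4. The plan's figure.** 14 × 24 = 336 h, which reproduces SAP 7.13.1. The value printed in SAP 8 is 336 × 24 = 8,064 h, 24 times larger.

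**Step 5. Size for one subject if SAP 8 is applied with 336 h.** The final-visit times are assumed.
- Final visit at 192 h: 336 − 192 = 144 h.
- Final visit at about 72 h: 336 − 72 = 264 h.

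These are upper limits, because the subject's own Stage 7 would come somewhat after the visit.

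**Step 6. Disagreement is not required.** The clinician scores once a day. Three diary entries 6 h apart leave 24 − 12 = 12 h without an entry overnight. Assume that healing is uniform over the 24 h before the final visit and that no entry is made at or after that visit. The share of subjects whose healing falls after the last entry is then gap ÷ 24: 0/24 = 0%, 6/24 = 25%, 12/24 = 50%. These are assumptions, not estimates; the documents give no frequency.

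**Step 7. Group-level illustration.** No SD is stated. The power statement (144 subjects, 95%, read with the 41 h difference) implies SD = 41 ÷ [(1.960 + 1.645) × √(2/72)] ≈ 68 h. This is back-solved, belongs to the herpetic episode endpoint and is borrowed here. Simulation: normal durations, placebo mean 220 h (assumed), difference 41 h, values limited to 24–336 h, 75 per arm, 1,500 runs, Hodges-Lehmann and two-sided Wilcoxon at 0.05.

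| Share set to 336 h (Merlin / placebo) | Estimated shift | Power |
|---|---|---|
| 0% / 0% | −40 h | 95% |
| 5% / 5% | −40 h | 90% |
| 10% / 10% | −37 h | 82% |
| 20% / 20% | −31 h | 63% |
| 10% / 20% | −50 h | 96% |
| 20% / 10% | −20 h | 35% |

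If the same subjects instead had their own Stage 7 recorded 12 h later, power stayed at about 93–95%. Using 8,064 h in place of 336 h gave much the same shift and power, because both methods rest on ranks or medians; means and SDs in the tables would be distorted.

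**The case against.** A reader might infer that the diary definitely stops at the clinician's Stage 7 and that this completer will be entered at 336 h. The documents do not settle either. The SAP sentence stands in a design summary, the Protocol continues the diary to healing, and SAP 9 says that no departures from the Protocol's analyses are planned. SAP 7.13.1 imputes only drop-outs, and SAP 7.1.2 on its face excludes diary endpoints altogether. Both objections stand. They leave the stop rule unreconciled and the outcome undetermined: missing, censored or imputed.

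A reader might also infer that the diary endpoints cannot then confirm or contradict the clinician. That goes too far. With three entries a day against one clinic score, a subject can record Stage 7 before the visit that detects it; what is lost is healing recorded later than that visit or after the last entry. Nor do the documents show that quick healers are affected as often as slow ones: follow-up to at least Visit Day 3 gives the earliest healers extra diary time.

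Finally, these are third-tier endpoints, and the sizes above rest on assumed times and frequencies. That is correct and limits the weight of the point. It does not supply the missing rule.

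**Conclusion.** The point holds in a limited form. The SAP ends the diary at a visit fixed by the clinician's score, the Protocol's stop rule differs and names no assessor, and a completer whose last diary stage is below 7 has no derivable value for two subject-assessed durations. The imputation provisions conflict. SAP 8, followed literally, would give that completer a false maximum duration, while in EE the value would be absent.

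The size is conditional. An overstatement of up to 144 h holds for an assumed final visit at 192 h and only if SAP 8 prevails with 336 h. The loss of power from about 95% to 82% holds only under the simulation's assumptions with 10% of each arm affected. The true frequency is unknown. The clinician-assessed primary and secondary efficacy endpoints are untouched. The change is worth making because it is specific and cheap.

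**What to change.** 1. **Protocol 4 and 7.2.5, SAP 2.2:** state one stop rule. Diary staging continues until the subject's own Stage 7 or Day 14, whichever is earlier, with an entry at the final clinic visit and a stated way to return the diary if it runs on afterwards.
2. **SAP 7.1.2, 7.13.1 and 8:** give one imputation scope. Limit 336 h to subjects who drop out before healing, and correct 336 days to 336 hours in section 8.
3. **SAP 7.13.1 and 7.13.5:** for subject-assessed complete healing and episode duration, treat a completer whose diary ends below Stage 7 before Day 14 as censored at the last diary entry, and analyse these endpoints by Kaplan-Meier and log-rank. SAP 6.1.4 already censors pain duration at the last pain assessment when pain has not resolved by 14 days.

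Two other repairs should be avoided. Using the final-visit time as the subject's healing time in the Wilcoxon test counts an unhealed subject as healed and substitutes the clinician's timing. Asking for the hour of healing at the safety call relies on two to three weeks' recall and sits badly with the bar on retroactive diary changes.

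Cost: a few extra diary entries for some subjects, a return route for the diary, and minor wording in both documents. Censoring so close to healing may be informative, which is a further reason to collect the subject's own Stage 7 wherever possible.

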### 3 Sample Size

The sample size for this study was based upon the results of the previous Phase 2 study, TR-H-211. In that study, Merlin demonstrated a statistically significant ( $p=0.0276$ ) effect on the duration of classical lesion endpoint for subjects beginning treatment at Stage 1 (erythema) with only 32 subjects treated with Merlin and 22 placebo subjects. Clinical investigations with Famvir and other independent studies, that initiate treatment within hours of the onset of prodromal symptoms (Stage 0) have demonstrated that 1/3 of all subjects enrolled in herpes labialis studies will have spontaneously aborted lesion. Any calculation of clinical trial size, therefore, must consider that factor. When, however, treatment is initiated at the erythema stage (Stage 1), as in the Merlin Phase 2a (TR-H-211) study, the incidence of spontaneously aborted lesions declines to 25%. As a result, a larger percentage of subjects will demonstrate classical lesions in Merlin studies than was seen in the Famvir, or similar previous studies. This was factored in when performing power calculations for this Phase 2b clinical study. Those calculations determined that 144 subjects would provide a 95% likelihood of statistical significance for the herpetic episode endpoint. Merlin decreased the duration of herpetic episode in subjects that began treatment at stage 1 by 41 hours, with a p-value of 0.055 in the Phase 2a study. The herpetic episode endpoint includes the subjects with aborted lesions.

As a result, a 150 subject clinical trial will have approximately 60 subjects progress to classical lesions in each treatment group and we can be very confident of having the power to demonstrate a highly significant difference for the duration of classical lesion endpoint, as shown in the Phase 2a results. In addition, a 150 subject clinical trial should have greater than 95% likelihood of demonstrating a statistically significant Merlin effect on herpetic episode as a secondary endpoint.

### 4 Inclusion/Exclusion Criteria

#### 4.1 Inclusion Criteria

1. Subject has a visible herpes simplex labialis lesion, in an area around the mouth, assessed by the subject, and confirmed by telephone contact, to be at the erythema stage (Stage 1) or Papule/Edema stage (Stage 2) as defined below:  
**Stage 1:** **Erythema stage** is defined as any redness with no skin swelling or other signs of advanced stages.  
**Stage 2:** **Papule/Edema stage** is defined as any skin swelling or solid raised area above the normal surface without evidence of more advanced stages such as fluid filled blisters.
2. Female subjects must be using a medically acceptable form of birth control during the study. Acceptable birth control measures include but are not limited to: abstinence, oral contraceptive pills or patch, injectable contraception, barrier contraceptives (condom, diaphragm with spermicide), intrauterine device, vaginal

contraceptive ring, surgical (hysterectomy, tubal ligation), vasectomized partner, and natural post-menopausal inability to conceive. Menopause is defined for this protocol as starting one year after the time of the last menstrual period.

3. Subject has immediate access to the kit containing the clinical trial material. (The subject will demonstrate access to the clinical trial material kit by reading the Randomization Number printed on the label on the kit.)
4. Subject is able to appear for a clinic visit within 24 hours from the time of enrollment into the Treatment Phase of the study (from the time the subject called to establish entry into the Treatment Phase of the study) and is able to return to the clinic for the full 14 day duration of the study if necessary.

